5 SUBJECT POPULATION

The target population for this study is adults, aged 18 and older, who are suffering from GERD and are newly diagnosed as partial responder to optimized PPI treatment. Subjects must meet all of the following inclusion criteria to be eligible for enrollment into the study:

Inclusion Criteria:

1. Provision of signed informed consent.
2. Able to read and write in French and able to comply with study requirement.
3. Female or male, aged 18 years or above.
4. The patient must at the enrolment visit be identified for the first time as partial responder to PPI treatment as defined by the following criteria:
 - a) At least 6 month history of GERD symptoms (need not be consecutive)
 - b) Continuously treated with unchanged optimized PPI treatment for any GERD indication during the last 4 weeks (an optimized PPI treatment is a treatment, which according to the investigators judgment cannot be further improved by changing brand or dosing of the PPI) .
 - c) Patients with a history of reflux (erosive) esophagitis Los Angeles grade A-D must have been continuously treated with a PPI during the last 8 weeks before enrolment (optimized PPI treatment during the last 4 weeks before enrolment).
5. To be eligible for enrolment, the patients must have reported, in the RDQ-RI screening instrument using 7 days recall, a minimum of three days with at least one of the two following symptoms with at least moderate severity:
 - a burning feeling behind the breastbone
 - an unpleasant movement of material upwards from the stomach.

Exclusion Criteria:

1. Patients that have not experienced any GERD symptoms improvement at all during PPI treatment.
2. Prior surgery of the upper GI tract (open, endoscopic and laparoscopic surgery on the esophagus, the stomach and the duodenum with the exception of over sewing or endoscopic treatment of an bleeding ulcer)

-
3. Any other condition which in the opinion of the investigator would render the patient unsuitable for inclusion in the study.
 4. Involvement in the planning or conduct of the study.
 5. Previous enrolment in the present study.
 6. Involvement in any other observational or clinical study at the time of this study.

6 SAMPLE SIZE

The target enrollment sample size for this study is 275 patients with GERD. An attrition rate of approximately 30% over the course of the twelve-month data collection period is expected as some patients will not complete and return the follow-up patient surveys, yielding a final sample size of ~200 patients for analysis.

Due to the descriptive objectives of the study, there are no hypotheses to test with statistical methods to predetermine a required sample size. Calculations based on a database study in the relevant patient group indicate that the sample size will result in satisfactory precision in estimates of individual items of resource utilization, symptom load, impact of symptoms on daily life and effect on work productivity.¹⁷ Based on previous similar studies in other but related patient groups the sample size is also deemed to be sufficient to satisfactorily describe common treatment pathways.

7 STUDY PROCEDURES

7.1 Site Recruitment

Potential investigators will be identified from a global French database provided by Rosenwald and compiling more than 160 000 physician references. A representative sample of 500 physicians including both general practitioners (family doctors and internists) and specialists, i.e. gastroenterologists, will be extracted and invited to participate in this study. The assumed ratio between specialist and general practitioner is 1:1. A mass mailing will be sent out to gauge investigator's interest and to evaluate their ability to successfully participate.

All interested sites, sorted by region, will be assigned a random number and will then be sorted by ascending order. The first 50 sites will be selected to participate. In case of any change in site's willingness to participate the site number 51 will be contacted to supplement the list and then 52, 53 subsequently.

7.2 Site Training

The study physicians and designated staff will be responsible for recruiting subjects, obtaining informed consent, and collecting baseline subject information. Study physicians and designated staff will be required to complete study training prior to recruitment of study subjects. Physicians and designated staff will receive training via participation in one of a series of scheduled web-ex training presentations. Training provides step-by-step instructions on how to recruit patients for the study, obtain informed consent, complete the CRF, report medical events, and retain study documents.

7.3 Subject Recruitment

Subjects will be recruited in community practice settings by approximately 50 study physicians in France. The target recruitment goal for each physician is 5 to 6 patients with GERD newly identified as partial responders with an upper limit of 14 per physician. Subjects will be enrolled during a normally scheduled office visit.

Enrollment will be closed once the target enrollment goal of 275 patients has been reached. Study physicians will be notified by telephone and fax memo that recruitment is closed.

7.4 Enrollment Visit: CRF

The study physicians will identify eligible patients at regularly scheduled office visits. Upon determining that the patient has at least 6 month history of GERD and has been identified as a first time partial responder to optimized PPI treatment, the study physician and/or designated staff will attempt to recruit the patient for the study. If a patient indicates that he or she is interested in participating, the physician will advise the patient of the nature of the study, study requirements, and study benefits using a study recruitment packet. The recruitment packet will include a study description, copy of the informed consent form, and a copy of the baseline patient survey.

The physician will ensure that the subject is given full and adequate oral and written information about the nature, purpose, possible risk and benefit of the study and will ensure that the subjects are notified that they are free to discontinue from the study at any time. This will also ensure that the subject is given the opportunity to ask questions and allowed time to consider the information provided.

The study physician will obtain informed consent from the patient and have the patient sign two copies of the informed consent form (ICF), one set of copies will be given to the patient to keep

and one set will be filed with the study materials for that patient. Signed and dated informed consent must be available before any other study procedures are conducted. Each patient will have a unique identifier assigned at the enrollment visit that will be used for all electronic and hard copy documents. Patients will officially be recruited in the study once they sign the informed consent form.

In order to finalize the screening process, the physician will confirm that the patient meets all study criteria as outlined in the CRF. Once this has been confirmed, the patient will, as a second step, complete the RDQ-RI. To be eligible for enrolment, the patients must have reported in the RDQ-RI screening instrument, using 7 days recall, a minimum of 3 days with at least one of the two following symptoms with at least moderate severity:

- a burning feeling behind the breastbone;
- an unpleasant movement of material upwards from the stomach.

The study physicians will also complete the visit 1 of the CRF for each subject to document enrollment into the study.

All subjects for whom a signed informed consent form and a completed baseline CRF, proving eligibility of the patient, are submitted will be considered enrolled in the study. Baseline CRF pages will also be collected for patients who fail study eligibility. The baseline RDQ-RI won't be collected for patient failing to one or more inclusion criteria from the baseline CRF. However, the baseline RDQ-RI will be collected for all the patients meeting all other baseline entry criteria, whatever there eligibility on this specific instrument (RDQ-RI).

7.5 Enrollment Visit: Patient Survey

At the time of the enrollment visit, study physicians and/or designated staff will provide to each subject a paper patient survey.

Sites will provide a private place, where subjects are not distracted and can concentrate on the completion of the questionnaires. Subjects will be asked to complete the general Health-related Quality of Life questionnaires first, followed by the disease specific questionnaires. After completion of the survey, subjects will be asked to return the completed documents to site staff in a sealed envelope for mailing back to i3. The package that will be mailed back to i3 will also contain the baseline RDQ-RI.

7.6 CRF: Resource utilization

The study physician will complete a hard copy CRF documenting the patient's medical resource utilization related to GERD such as office visits, prescriptions, hospitalizations etc at month 6 and 12 following study entry. Data regarding over the counter medication and visit to other

physicians will be collected from the patient directly via the patient survey document at month 3, 6, 9 and 12 from study entry.

7.7 Log of new GERD patients

A log of all newly diagnosed patients with GERD seen in the physician's office will be maintained during the duration of patient enrollment. This paper-based log will contain the following data fields to allow for the estimate of a ratio of all newly diagnosed patients with GERD and first time partial responders:

- Patient year of birth
- Patient gender
- Date of first GERD diagnosis / Date seen in Practice

This log will be returned to i3 at the end of enrollment period. A copy of the log will be kept on site.

7.8 Follow-Up Patient Mail Surveys

Quarterly follow-up patient surveys will be mailed to patients by the physician. In addition to the same set of self-administered questionnaires as completed during the initial visit, the package will also include an additional one or two pages dedicated to resource utilization data for over the counter medication and visits to other physicians.

Patients will return the completed survey by mail in a postage-paid return envelope to the CRO in charge of the data collection (i3).

To limit the number of non-responders to quarterly follow-up surveys, a reminder call will be placed to the study physician two weeks before the scheduled date. Upon the sites' confirmation, a second package will be sent to the sites for non-responders two weeks after the initial mailing, and will contain the same contents as the initial packet. Patients may be called to remind them to complete the surveys.

7.9 Study Assessments

Data will be collected using a case report form, a patient baseline survey, and four follow-up patient surveys at 3, 6, 9 and 12 months. A summary of each assessment appears in the sections below.

Schedule of Completion	Total Questions	V1	3 months	6 months	9 months	12 months
Physician CRF						
Eligibility and demographics, history, comorbidities	20	X				
Physician CRF / Patient Survey:						
Resource Utilization						
Hospital visits, physician's office visits, prescriptions	~10	X		X		X
Patient Survey:						
Resource Utilization						
Over the counter medication, other physicians			X	X	X	X
Anxiety & Depression						
Hospital Anxiety and Depression Scale (HADS)	14	X				X
Symptom Frequency and Severity						
Reflux Disease Questionnaire (RDQ-RI)	26	X	X	X	X	X
GERDQ	6	X		X		X
Quality of Life						
Quality of Life in Reflux and Dyspepsia (QOLRAD-RI)	25	X		X		X
EQ-5D	6	X		X		X
Short Form 36 (SF-36)	36	X		X		X
Work Productivity						
Work Productivity and Activity Impairment for Patients with Gastroesophageal Reflux Disease (WPAI-GERD)	6	X	X	X	X	X

7.9.1 Case Report Form (CRF)

The CRF will collect the following data:

1) Enrollment visit

- Patient characteristics:
 - gender
 - year of birth
 - height and weight
 - waist circumference
 - highest level of education
- Clinical information:
 - GERD treatment and history
- Concurrent medical conditions (e.g., hypertension, lipid metabolism disorders, heart disease, upper GI disorders) and medications;
- Type and dosage of PPI, duration of treatment

2) During the study

Additionally, the study physician will complete a CRF at month 6 and month 12 during the study using information from the patient's medical records to collect the following information:

- diagnostic procedures
- endoscopic procedures (e.g. endoscopy with or without biopsy, dilation of stricture),
- presence of Barrett's epithelium
- hospitalizations, emergency room, and office visits due to GERD
- specialist referrals due to GERD
- prescriptions for GERD

7.9.2 Patient Baseline and Follow-Up Surveys

The patient survey will include the following patient reported outcomes questionnaires:

Symptom Frequency and Severity

- The Reflux Disease Questionnaire (RDQ-RI) is a 26-item, self-administered questionnaire designed to assess the frequency and severity of heartburn, acid regurgitation and epigastric pain over the previous week¹⁹. A GERD dimension can be obtained by combining the heartburn and regurgitation dimensions, while the epigastric pain dimension is also known as the dyspepsia dimension.

Symptom frequency and severity are scored on a 6-point Likert scale, with higher scores indicating more frequent or severe symptoms.

- The GERDQ is a 6-item questionnaire that measures symptoms in the upper gastrointestinal tract.

Quality of Life

- The Quality of Life in Reflux and Dyspepsia – Reflux Inhibition (QOLRAD-RI) questionnaire is a disease-specific quality of life instrument comprising 25 items that ask subjects about the effect of upper gastrointestinal symptoms on five dimensions: emotional well-being, sleep, vitality, eating/drinking and physical/social functioning²⁰. Subjects report the frequency of these effects during the previous week using a 7-point Likert scale, ranging from one (all of the time/a great deal) to seven (none of the time/none at all), with low scores indicating a severe impairment of daily functioning.
- The SF-36 is a 36-item general quality of life instrument that measures physical functioning, bodily pain, and role limitations due to physical health problems, role limitations due to personal or emotional problems, emotional well-being, social functioning, energy/fatigue, general health problems, and perceived change in health. It yields an eight-scale profile of functional health and well-being scores as physical and mental health summary measures and a preference-based health utility index.²¹ Item response categories range from dichotomous to six levels and are scored so that a higher score indicates a more favorable health state.
- The EQ-5D is a health-outcome measure that provides a descriptive profile and index value for health status.²² Five questions comprise dimensions of health (mobility, self-care, usual activities, pain/discomfort, anxiety/depression) across three levels (no problems, some/moderate problems, and extreme problems), in addition to one measure of health status on a vertical graduated (0-100) visual analog scale.

Anxiety and Depression

- The Hospital Anxiety and Depression Scale (HADS) is a 14-item self-assessment designed to detect states of anxiety and depression among patients in an outpatient clinic setting.²³ Each item is answered by the patient on a four point (0–3) response category. The HADS yields an anxiety score and a depression score.

Work Productivity

- The Work Productivity and Activity Impairment for Patients with Gastroesophageal Reflux Disease (WPAI-GERD) questionnaire is a six question instrument that measures work productivity and activity impairment instrument over the past seven days due to GERD.²⁴ It yields four types of scores; absenteeism (work time missed), presenteeism (impairment at work / reduced on-the-job effectiveness), work productivity loss (overall work impairment / absenteeism plus presenteeism) and activity impairment. WPAI outcomes are

expressed as impairment percentages, with higher numbers indicating greater impairment and less productivity.

Patient resource utilization

A patient resource utilization instrument investigating about any over the counter medication taken by the patient during the 12 months during the study, as well as visits to other physicians will be provided to the patient together with the survey at month 3, 6, 9 and 12. A memory aid will allow the patient to track their medication between the survey dates.

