10.7 Cost of Illness Analysis

The first step of this analysis will consist of estimating the size of the target population. A literature review will be undertaken to obtain the incidence and prevalence of GERD in France and the proportion of patients treated in primary care and secondary care. The proportion of

patients with GERD with incomplete response to PPI will be calculated from the sites' log. The proportion of partial responders will be reported by site, physician type and overall, together with 95% confidence intervals. The size of the target population (partial responders to PPI) in France will then be derived.

Based on the information obtained from the cost of healthcare resources collected alongside this study, we will be able to estimate the cost of partial response to PPI within the year of partial response diagnosis. Some assumptions will be made on the basis of the literature and clinical experts' opinion to estimate the mean cost of treatment over subsequent years. The cost of partial response to PPI will be reported overall and by type of resource (GP visits, specialist visits, diagnostic tests, hospitalization, prescribed medications and OTC medications) for France.

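### The memory aid is described for medication only, so visits to other physicians rest on patient recall, while the same visit type comes from records when the enrolling physician provides it

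*Protocol*

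**What the plan says.** Section 7.9.2 describes a single patient instrument for two items. It asks about over-the-counter medication, "as well as visits to other physicians will be provided to the patient together with the survey at month 3, 6, 9 and 12". The aid that goes with it is described in one sentence: "A memory aid will allow the patient to track their medication between the survey dates". Section 7.6 confirms that both items come from the patient: the data "will be collected from the patient directly via the patient survey document at month 3, 6, 9 and 12".

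The study physician has a different source. Under section 7.9.1 the month 6 and month 12 CRF is completed "using information from the patient's medical records to collect the following information", and the list includes "hospitalizations, emergency room, and office visits due to GERD" and "specialist referrals due to GERD".

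Section 7.1 recruits both general practitioners and gastroenterologists, in an assumed 1:1 ratio. Section 10.3 reports resource use by physician type and overall, and section 10.4 does the same for mean cost. Section 10.7 reports the cost of partial response overall and "by type of resource (GP visits, specialist visits, diagnostic tests, hospitalization, prescribed medications and OTC medications"), so GP visits and specialist visits are separate lines.

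**The concern.** The protocol recognises that memory between surveys needs support and then supports one of the two items asked for. Nothing in sections 4, 7.6, 7.8, 7.9 or 7.10 describes a diary or a record check for visits to other physicians.

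The gap matters because the source of a visit depends on who enrolled the patient. A visit to a gastroenterologist is taken from records if that gastroenterologist is the study physician, and is reported by the patient if a GP is. GP visits run the opposite way. The measurement method is thus tied to enrolling physician type, which is one of the planned reporting axes.

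Collecting resource use and calculating cost per patient are primary objectives (section 3.1). A visit that nobody recorded cannot be recovered in the analysis, so this cannot be left to the statistical analysis plan.

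**Working it through.** The plan states no figure on this point, so there is none to reproduce. The check compares sources and then asks how large an effect could be.

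**1. Source of each visit type, by enrolling physician (sections 7.6, 7.9.1, 7.9.2)**

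| Visit type | Patient enrolled by a GP | Patient enrolled by a gastroenterologist |
|---|---|---|
| GP visit | Records (study physician) | Patient survey |
| Gastroenterologist visit | Patient survey; referral on the CRF | Records (study physician) |

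The table covers record-based visits to the enrolling physician. A second GP or a second gastroenterologist would also count as another physician. Each group has one visit type that relies on the patient, so the problem runs both ways.

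**2. Scope.** The record items are limited to GERD (sections 7.6 and 7.9.1). The patient item on visits carries no such limit in section 7.6 or 7.9.2. This second difference between the sources could raise the patient-reported count.

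**3. Whether these visits are costed.** Section 10.4 opens by naming two inputs: physician-reported use, and patient-collected over-the-counter medication. Patient-reported visits are not among them. Later in the same paragraph, unit costs are applied to use that the patients report. The two sentences do not agree. If patient-reported visits are costed, recall error reaches the visit lines of section 10.7. If they are not, the cost problem is omission of outside visits instead.

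**4. Patient split.** Taking the 50 physicians of sections 7.1 and 7.3 and the midpoint of the target of 5 to 6 patients, 50 × 5.5 = 275, the enrolment target. An even physician mix would then give 25 × 5.5 = 137.5 patients per type. The protocol does not fix this split:
- The 1:1 ratio is an assumption about physicians, and sites are selected by random number with no stated stratification by specialty. From an even pool, the 95% binomial range for the number of GPs among 50 sites is 18 to 32.
- With the cap of 14 patients per physician, 25 sites of one type could enrol 25 × 14 = 350, more than all 275.

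**5. Illustration (all rates assumed).** Let *f* be the share of outside visits forgotten and *p* the share of all visits of a type that come from the patient. Assume complete records, no over-reporting and equal true rates in both groups.
- For specialist visits, the ratio of GP-enrolled to gastroenterologist-enrolled patients reads 1 − *f*. For *f* = 10%, 20% and 30% it is 0.90, 0.80 and 0.70.
- The understatement of the whole visit line is *p* × *f*:

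| *p* | *f* = 10% | *f* = 20% | *f* = 30% |
|---|---|---|---|
| 0.3 | 3% | 6% | 9% |
| 0.5 | 5% | 10% | 15% |
| 0.7 | 7% | 14% | 21% |

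Neither *f* nor *p* is in the protocol. A share of patients is also not a share of visits: if gastroenterologist visits cluster in patients whom gastroenterologists enrolled, *p* for that line is lower than the GP-enrolled share of patients.

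**The case against.** The strongest reply is that no error is shown. Quarterly patient report of outside visits is ordinary practice. Over-the-counter use is frequent and has no record source, so it is reasonable to aid that item first. Neither the instrument nor the aid is shown, one sentence on purpose need not list all its contents, and no recall window for visits is stated. This stands in part: three months is read from the survey spacing. Even so, the text names medication only, and if the aid also covers visits the protocol should say so.

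A second reply is that records do cover some outside use. The section 7.9.1 list is not expressly confined to the enrolling practice, it includes specialist referrals for every patient, and the schedule in section 7.9 heads the office-visit row as both physician CRF and patient survey. This also stands in part. However, a referral is not a visit count. It misses repeat and self-initiated visits, and it says nothing about GP visits in gastroenterologist-enrolled patients.

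Third, the direction is open. Forgetting lowers the count, but misdating a visit into the window or reporting one unrelated to GERD raises it, and records may themselves be incomplete. This stands in full.

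A reader might go further and infer that half of the sample is affected, or that each visit line is understated by 5% to 15%. The documents do not support either. The 1:1 ratio concerns physicians, and the percentages multiply two assumed quantities.

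**Conclusion.** The point holds as a cheap improvement to data capture. As the protocol is written, visits to other physicians rely on patient recall between surveys without the aid given for medication, and a GP or gastroenterologist visit has a different source depending on who enrolled the patient. CRF referrals soften this for specialist use in GP-enrolled patients.

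Reported visit use by physician type can be distorted. The two visit cost lines can be distorted by recall only if patient-reported visits enter the costing, which section 10.4 leaves unsettled. The protocol does not give the size or the net direction. An understatement equal to the forgotten share of outside visits is an illustration that assumes complete records and no over-reporting. It is not an estimate of bias in this study.

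**What to change.** In section 7.9.2, extend the existing memory aid so that the patient notes each visit to another physician between surveys: date, type of physician, and whether it was due to GERD (yes/no). The patient then transfers these entries to the quarterly survey. The GERD field allows the patient-reported visits to be brought to the same scope as the CRF items.

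In section 10.4, reconcile the two sentences on cost inputs and state whether patient-reported visits are costed.

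The cost is one more block on a form that patients already receive, with slightly more burden for them and no added visit, procedure or staff. Aided patient report would still be compared with medical records, so the difference in source is reduced but not removed, and results by physician type should carry that caveat.
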